5.12.4 Assessment of Adverse Event Relationship to Study Medication

The relationship of an AE to investigational product(s) will be classified using modified World Health Organization (WHO) criteria (Edwards and Biriell, World Health Organization Collaborating Centre for International Drug Monitoring 1994) as follows.

Related: a clinical event, including laboratory test abnormality, with a reasonable time sequence to administration of the drug, unlikely to be attributed to concurrent disease or other drugs or chemicals, and which follows a clinically reasonable response on withdrawal (dechallenge). Rechallenge information is not required to fulfill this definition; or an event that could also be explained by concurrent disease or other drugs or chemicals where information on drug withdrawal may be lacking or unclear.

Not related: a clinical event, including laboratory test abnormality, with sufficient evidence to accept that there is no causal relationship to drug administration (e.g., no temporal relationship to drug administration, because the drug was administered after onset of event; investigation shows that the drug was not administered; proof of other cause; etc.); or an event with a temporal relationship to drug administration which makes a causal relationship improbable, and in which other drugs, chemicals or underlying disease provide plausible explanations.

5.12.5 Assessment of Adverse Event Outcome

Outcome of AEs will be defined based on ICH Topic E2B, ICH Guideline.

- Recovered/Resolved
- Recovered/Resolved with Sequelae
- Recovering/Resolving
- Not Recovered/Not Resolved
- Fatal
- Unknown

5.12.6 Action Taken for Adverse Event

Action taken for AEs will be documented in the eCRF according to the following:

- Concomitant medication or other treatment
- Withdrawal from study

5.12.7 Action Taken for Study Drug

Any action taken with study drug will be defined based on ICH Topic E2B, ICH Guideline and documented in the eCRF according to the following:

- Drug Withdrawn
- None (not changed)
- Dose Reduced
- Unknown
- Not Applicable

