4.6.1 Dose Interruption and Stopping Rules

Adverse Events (AEs) of supine SBP decrease, supine DBP decrease, postural BP decrease, HR increase and HR decrease will be closely monitored. If such an AE occurs in patients taking the study drug, the Investigator must assess whether the AE meets the study drug interruption/stopping rules and proceed as recommended in the below table.

If the study drug is interrupted due to the criteria described in the table, the patient will be evaluated as part of an unscheduled visit to assess their status and the Investigator will determine next course of action. If necessary, subsequent visits to assess the outcome of the event will be scheduled. Once the re-start criteria are met, study drug will be re-started under medical supervision. Additional visits may be scheduled at the investigator's discretion to more closely monitor patient status.

Any patient that develops postural hypotension will not be discharged from the study site with study drug until the event completely resolves and safety and tolerability of the reduced dose in the patient is confirmed.

Amendment 02 (10 August 2017)

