3.3. Study Endpoints

3.3.1. Primary Endpoints

There is no primary endpoint in this study.

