9.1. Adverse Events

AEs will be coded using MedDRA (Version 21.0) and tabulated, including categorical information of interest such as onset and resolution times, time of onset relative to dose, severity at onset, maximum severity, causal relationship to study medication, and action taken. AEs will be regarded as 'pre-treatment' if they occur between Screening and the time of administration of the first dose of APD371 and will be recorded as medical history. All other AEs that occur after the first dose of study medication will be considered to be 'treatment'.

Treatment-emergent AEs (TEAE) will be listed by subject and by treatment. They will be summarized per treatment and expressed in terms of maximum severity and relationship to study medication. The incidence of TEAEs classified according to system organ class will be summarized by treatment group. TEAEs will also be summarized by maximum intensity (assessed according to the Common Terminology Criteria for Adverse Events v4.032 definitions) and relatedness to study medication.

Summaries of the number (%) of subjects in each treatment group with at least one TEAE, classified according to MedDRA system organ class (SOC) and preferred term (PT), will also be provided for:

- Drug-related TEAE
- TEAEs leading to permanent discontinuation of study medication (study medication discontinued or withdrawal from study).
- Serious adverse events (SAEs)

SAEs will be listed by subject and by treatment. If there are no SAEs at the end of the study, the tables or listings will state that there are no SAEs in the study.

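### The action-taken list has no code for drug interruption although Protocol 4.6.1 provides for it, so interruptions caused by adverse events cannot be tabulated as a tolerability outcome

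*Protocol*

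**What the plan says.** **The rule.** Protocol 4.6.1 covers adverse events of falling supine or postural blood pressure and of rising or falling heart rate. For these, "the Investigator must assess whether the AE meets the study drug interruption/stopping rules and proceed as recommended in the below table". It continues: "If the study drug is interrupted due to the criteria described in the table, the patient will be evaluated as part of an unscheduled visit". Re-start under medical supervision follows once the re-start criteria are met. The same section also refers to stopping and, after postural hypotension, to a reduced dose. The governing table is not shown in the public document.

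**The record.** Protocol 5.12.7 states: "Any action taken with study drug will be defined based on ICH Topic E2B, ICH Guideline and documented in the eCRF". Its five codes are *Drug Withdrawn*, *None (not changed)*, *Dose Reduced*, *Unknown* and *Not Applicable*. The separate field in Protocol 5.12.6, for action taken on the event itself, has two entries: "Concomitant medication or other treatment" and withdrawal from the study.

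**The analysis.** Protocol 8.6.1 and SAP 9.1 both say that adverse events will be tabulated with, among other items, the action taken. The one drug action for which SAP 9.1 specifies its own TEAE summary is: "TEAEs leading to permanent discontinuation of study medication (study medication discontinued or withdrawal from study". SAP 3.1 and 4.2, describing the response to hypotensive symptoms, mention only a step down from 100 mg to 50 mg. Tolerability and safety are the primary objective (Protocol 2.1, SAP 2.1).

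**The concern.** The protocol directs an action that its own form cannot record. A site that follows 4.6.1 exactly, and then completes 5.12.7 exactly, must enter a wrong code or one that drops the interruption. That field feeds a planned tabulation, and the subject is tolerability, the study's primary objective.

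Needing to stop a drug temporarily because of an adverse event is a direct sign of how well a dose is tolerated. Protocol 3.3 says the study is to guide dose and regimen choices in later studies. If temporary holds cannot be counted by dose, that choice rests on permanent discontinuations and event counts, without the intermediate outcome that 4.6.1 itself creates.

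**Working it through.** The documents state no figure on this point and made no power calculation (Protocol 8.2), so there is nothing to reproduce. The check sets the texts side by side and then gives the scale.

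**Step 1. Drug actions in 4.6.1 against codes in 5.12.7**

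| Course after the event | Fitting code | What is lost |
|---|---|---|
| Stopped for good | *Drug Withdrawn* | Nothing |
| Dose reduced without a hold | *Dose Reduced* | Nothing |
| Held, re-started at a lower dose | *Dose Reduced* | The hold |
| Held, re-started at the same dose | None | The hold; the entry would be *None (not changed)* or *Unknown* |

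Codes for interruption: 0 of 5 in Protocol 5.12.7 and 0 of 2 in Protocol 5.12.6.

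**Step 2. Do other planned outputs recover the link from event to hold?**

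- TEAE tables by preferred term, severity and causality (SAP 9.1, 13) and the orthostatic hypotension and postural tachycardia summary (SAP 9.2.2) show that an event occurred. They do not show that drug was held.
- Exposure and compliance (SAP 7.2, 7.3) would fall after a hold, but give no cause. Section 13 assigns both tables to the Efficacy population, which requires at least 7 days of on-treatment pain scores up to Week 4 (SAP 4.5). A subject who stopped recording before that would be left out.
- Drug-accountability records give the reasons for departures from expected dispensing (Protocol 4.4). They are a source for reconstruction; no summary of them is planned.

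**Step 3. Compliance.** SAP 7.3 divides capsules taken by capsules due over the days in the active treatment phase, with no stated exclusion for held days. Assume one capsule per dose, held days left in the denominator, and no other missed doses:

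- Capsules due: 56 × 3 = 168. The 80% threshold in SAP 5.3 is 0.80 × 168 = 134.4.
- 11-day hold: (168 − 33)/168 = 135/168 = 80.4%.
- 12-day hold: (168 − 36)/168 = 132/168 = 78.6%.

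On that reading, a hold of 12 days or more made under the protocol's own rule is reported as a significant protocol violation.

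**Step 4. Scale.** Protocol 4.6 plans 8 subjects per cohort.

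- One hold is 1/8 = 12.5 percentage points of a cohort, or 1/16 = 6.25 points overall.
- Recorded, it reads 1/8 = 12.5% (exact 95% interval 0.3% to 52.7%). Unrecorded, it reads 0/8 = 0% (0% to 36.9%).
- The chance of at least one hold in a cohort is 1 − (1 − p)⁸. The documents give no p. For assumed rates of 5%, 10%, 20% and 30% the results are 34%, 57%, 83% and 94%.

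**The case against.** The strongest reply is that little of clinical importance goes unseen. Every event after dosing is a TEAE (Protocol 5.12.1). Orthostatic hypotension and postural tachycardia are counted by treatment at all timepoints, with categorical tables, a listing and individual profiles. With about 16 subjects, holds can probably be reconstructed one by one from dosing, accountability and visit records. This stands, and it limits the point to the missing link between an event and a temporary hold. A reader might infer that the trial misses the hypotension or heart-rate events themselves; the documents do not support that.

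Second, a reader might take interruption and re-start to be the main response under 4.6.1. The governing table is not shown, the section also covers stopping and reduction, and the SAP describes only down-titration. How often a hold would end in re-start at the same dose, or whether the table allows it, is unknown. This also stands. It does not rescue the list, because a hold followed by a lower dose is lost as well.

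Third, Section 13 should not be read as proof that an analysis is missing: the permanent-discontinuation summary that SAP 9.1 does specify has no table title there either. The argument therefore rests on the code list and the text of SAP 9.1. A tabulation of action taken cannot show a category that was not collected.

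Fourth, the eCRF itself is not among the documents and may hold a field that the protocol does not list. The sponsor can check this.

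**Conclusion.** The point holds at moderate severity. The action-taken list cannot represent a response that the protocol provides for, and the only TEAE summary by drug action specified in SAP 9.1 is permanent discontinuation. Interruptions caused by adverse events therefore cannot be tabulated as a tolerability outcome from the field meant to record them. Each one missed is 12.5 percentage points of a cohort of 8. This assumes that the eCRF follows Protocol 5.12.7. The compliance side-effect also depends on held days staying in the denominator, which the SAP leaves open.

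Two further inferences are not supported:

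- **That the omission favours 100 mg.** SAP 3.1 and 4.2 attach down-titration for hypotension to the 100 mg group, but 4.6.1 applies to any patient on study drug, and the documents give no interruption rate by dose. The direction of any bias is unknown.
- **That the planned report would show no intolerant subjects.** The SAP plans no count of intolerant subjects. It does plan TEAEs by severity and relatedness, drug-related TEAEs and SAEs.

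**What to change.** 1. **Data still to be collected, if any:** add a drug-interrupted code, with stop and re-start dates, to Protocol 5.12.7 and the eCRF.
2. **Analysis:** add to SAP 9.1 and Section 13 one Safety-population table by randomised dose giving the number and percentage of subjects with a TEAE leading to interruption, to dose reduction, to permanent discontinuation, and to any of these.
3. **Data already locked:** the SAP's summary of changes gives lock on 14 September 2018 and relock on 19 November 2018, so a new code cannot reach these data. Derive interruptions from on-site dosing, drug-accountability and unscheduled-visit records, state the derivation rule, and label the table post hoc. SAP 3.3.1 says "There is no primary endpoint in this study"; this table should not be named as the tolerability endpoint now, since that would be choosing an endpoint after lock in an open-label trial.
4. **Compliance:** state in SAP 7.3 and 5.3 that holds directed by the protocol are not counted as non-compliance.
5. **Consistency:** reconcile Protocol 4.6.1 and 5.12.7 with SAP 3.1 and 4.2 on which drug actions apply. This review takes no view on which clinical rule is right.

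The cost is one code, one table and some derivation work on about 16 subjects. A dose's tolerability may look slightly less favourable once holds are counted.

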5.12.8 Collection of Extra Laboratory Samples/Investigations

In the event of a clinically important AE, a suitable sample may be collected for drug assay or for additional laboratory tests. The Investigator must ensure that the sample is properly labeled and stored. The Investigator and others responsible for care of the subjects should institute any supplementary investigations of significant AEs based on the clinical judgment of the likely causative factor. This may include seeking a further opinion from a specialist in the field of the AE. The Sponsor (or designee) may suggest special tests based on expert advice.

5.12.9 Follow-up of Adverse Events Present at Last Scheduled Study Visit

Adverse events present at the last study day (Wk8) that require follow-up or a repeat laboratory test will be assessed at the last Follow-up visit (Wk 10) and if still present will

continue to be followed-up for 30 days after the last day of study treatment, according to the CRO's procedures for AE follow-up.

Adverse events that have not resolved or stabilized at 30 days after the last subject's last study dose, will be reviewed with the Sponsor on an individual basis to determine if the database will be locked and subsequently updated once the events of ongoing AEs are resolved or if database lock will be held.

5.13 Concomitant Medications and Procedures

All medications (OTC and prescribed) that are taken by subjects and all procedures that are performed during the Screening period and during the study must be recorded in the eCRF with start date/time and stop date/time, if known.

5.14 Removal of Subjects from the Trial or Study Drug

The study will be terminated early if, in the opinion of the Sponsor, Investigator, or IRB, an unacceptable risk to the safety and welfare of subjects is posed by the continuation of the study in light of review of the key safety data.

Subjects will be informed that they are free to withdraw from the study at any time for any reason should they so wish. The Investigator may remove a subject if, in his/her opinion, it is in the best interest of the subject. A subject may be withdrawn from the study for any of the following reasons:

- Deviation/noncompliance with the protocol;
- A serious or intolerable AE occurs;
- The Sponsor or Investigator terminates the study; or
- Withdrawal of consent any subject may withdraw his/her consent from the study at any time. The Investigator should make a reasonable attempt to document the specific reason why consent is withdrawn.

5.14.1 Handling of Withdrawals

Although a subject is not obliged to give his/her reason for withdrawing prematurely, the Investigator will make a reasonable effort to obtain the reason while fully respecting the subject's rights. If there is a medical reason for withdrawal, the subject will remain under the supervision of the study physician until in satisfactory health. Reasonable efforts will be made to contact a subject who fails to attend any follow-up appointments, in order to ensure that he/she is in satisfactory health.

If a subject is prematurely discontinued from this study, the procedures described in Section 6.4 must be followed.

5.14.2 Replacements

Randomized and treated subjects who discontinue the study will not be replaced. Subjects who are randomized but are not treated or are withdrawn due to non-compliance or a major protocol deviation may be replaced.

5.15 Allowable Visit and Procedure Windows

The following are allowable windows for study visits and procedures:

- Study visits:
 - Wks 2, 4, 6, 8 and 10 (Follow-up): ± 2 days
- Vital signs and Active-Standing Test:
 - Pre-dose timepoint: 15 mins
 - Post-dose timepoints: $\pm 15 \text{ min}$

6 STUDY ACTIVITIES

6.1 Screening Visits Wk -4 to Wk -1 (Days –28 to -1)

Subjects with a signed ICF and undergoing planned screening will be allocated a sequential 4 digit screening number starting X001 by the investigator or designee.

Within 29 days and up to Day -1 before administration of the first dose of study medication, all Screening activities necessary to define eligibility for entry into the study will be conducted and consist of the following:

- Collection of demographic data (sex, age, race/ethnicity)
- Completion of medical and social history (to include tobacco, alcohol, and caffeine use)
- Body measurements
- Physical examination (complete examination) at initial screening visit
- Abbreviated physical exam (includes body weight and evaluation of changes to previously observed abnormal findings) at final screening visit
- Vital signs
- 12-lead ECG
- Virology screen (HBsAg, HIV antibodies, and HCV antibodies)
- Drugs of abuse screen
- Serum hCG pregnancy test (females only) at the initial screening visit
- Urine pregnancy test (females only) at the final screening visit
- Clinical laboratory tests to include hematology, serum chemistry, coagulation, HsCRP, thyroid function tests (TSH, T4, and free T4 at initial Screening visit only) and urinalysis.
- Stool sample for fecal calprotectin
- Total Simple Endoscopic Score (SES-CD) score < 10 or FCP < 500 mcg/g. Endoscopy results obtained within 1 month prior to screening may be utilized
- Abdominal Pain Assessment scores to be conducted on at least 7 consecutive days twice daily
- Monitor and document any pre-treatment AEs
- Concomitant medications assessment

At the end of Day -1 all subjects will have undergone screening assessments and final confirmation or otherwise of eligibility.

Subjects who are deemed eligible for the study will be randomized and then report to the study site on the morning of Wk 0 (Day 1) ready for an overnight stay. They will undergo pre-treatment assessments and then the first dose of study medication will be given in the morning at the study site.

6.2 Screening Failures

A Screening failure is defined as a subject who has signed the ICF, but does not meet all the entry criteria as outlined in this protocol and has not been randomized or received study medication. A Screening log will be maintained by the Investigator or designee, indicating the reason for the Screening failure.

6.3 Treatment Period Wk 0 to 8 (Day 1 to Day 56)

Subjects will self-administer APD371 TID for 56 consecutive days according to the randomization schedule. Study procedures will be conducted at the time points indicated in the Schedule of Events (Table 1) and include the following assessments;

6.3.1 Wk 0 (Day 1) Pre-treatment

- Vital signs and Active-Standing Test
- 12-lead ECG
- Abdominal Pain Score within 60 min prior to first morning dose
- PK Blood sample for the analysis of APD371 and metabolite plasma concentrations will be collected within 60 min prior to the first morning dose
- Clinical laboratory tests (to include hematology, serum chemistry, coagulation, HsCRP, and urinalysis)
- Record AEs
- Record concomitant medications
- Study medication will be dispensed before the first dose (Week 1-2)

6.3.2 Wk 0 (Day 1) Post treatment

- Vital signs and Active-Standing Test
- 12-lead ECG at 1.5 hours after initial Day 1 dose
- Abdominal Pain Score at 1.5 hr after first morning dose

- PK Blood samples for the analysis of APD371 and metabolite plasma concentrations 0.5, 1, 2, 4, 6 and 8 hr after the first daily dose (prior to second daily dose) and 9 and 10 hr.
- Record AEs;
- Record concomitant medications

6.3.3 Wk 0 (Day 2)

- Vital signs and Active-Standing Test
- Abdominal Pain Scores
- A PK Blood sample for the analysis of APD371 and metabolite plasma concentrations will be collected 24 hr post first daily dose on Day 1 and before the first daily dose on Day 2
- Record AEs
- Record concomitant medications
- 6.3.4 Wk 0 to 8 (Day -1) (Days 1 to 56)
 - Abdominal Pain Scores will be determined three times a day.

6.3.5 End of Wk 1, 2, 4, 6

- Vital signs and Active-Standing Test
- Abdominal Pain Scores
- PK blood samples will also be taken immediately before the first daily dose (Week 2, 4 and 6 only)
- Clinical laboratory tests (to include hematology, serum chemistry, coagulation, HsCRP, and urinalysis) prior to first morning dose, Wk 4 only
- Study medication will be dispensed before the first daily dose for Wk 0 (Day 1), 2, 4 and 6
- Compliance will be assessed based on all returned bottles and treatment duration at Wks 2, 4, 6 and 8
- Record AEs
- Record concomitant medications
- Stool sample for fecal calprotectin (Wk 4 only)

It is important that subjects do not take their morning study medication prior to instruction by the investigation team on Wk 0 (Day 1 and Day 2), 2, 4 and 6.

6.3.6 Wk 8 (Day -1)

- Vital signs and Active-Standing Test
- 12-lead ECG
- Clinical laboratory tests (to include hematology, serum chemistry, coagulation, HsCRP, and urinalysis) prior to first morning dose
- Abdominal Pain Score
- PK Blood samples for the analysis of APD371 and metabolite plasma concentrations will be collected prior to and at 0.5, 1, 2, 4, 6 and 8 hr after the first daily dose (prior to second daily dose)
- Stool sample for fecal calprotectin
- Colonoscopy for total Simple Endoscopic Score (SES-CD) score (optional)
- Record AEs
- Record concomitant medications

6.3.7 Wk 8 End of Treatment

- Vital signs and Active-Standing Test
- Abdominal Pain Score
- A PK Blood samples for the analysis of APD371 and metabolite plasma concentrations will be collected 8 hr post first daily dose on Wk 8 (Day -1)
- Record AEs
- Record concomitant medications

Each subject will be evaluated continuously by the Investigator and Sponsor with regards to safety, and then the decision will be made on a case-by-case basis on whether the subject needs to stay overnight at Week 8 to be assessed for safety, including blood pressure and heart rate. If the decision to remove the Visit 8 (Wk 8) overnight stay has been determined, all scheduled evaluations still must be done, including serial PK collections vital signs, active-standing test, APS.

detailed in the diary cards.

6.4 Early Termination Procedures

- Physical examination (abbreviated examination including body weight and evaluation of changes to previously observed abnormal findings)
- Vital signs and Active-Standing Test
- 12-lead ECG
- Serum hCG pregnancy test (females only)
- Final PK blood sample
- Clinical laboratory tests (to include hematology, serum chemistry, coagulation, HsCRP, and urinalysis)
- Abdominal Pain Score
- Record AEs
- Record concomitant medications

